16. SAFETY ISSUES AND MONITORING

There may be unexpected serious adverse reactions associated with melatonin when used in pregnancy. To date, clinical studies have not demonstrated any serious adverse reactions to melatonin, however metabolic changes during pregnancy may alter the pharmacological properties in unanticipated ways.

16.1 - Eliciting and documenting AE and SAE

The recording of adverse experiences is an important aspect of the trial's conduct. The lead PI responsible for trial-related medical decisions will be designated as the person responsible for the assessment, documentation and reporting of all events to the sponsor, Monash Health, that meet the definition of an AE, SAE or SUSAR. All site PI's are responsible for notifying the lead PI of SAE and SUSAR's as outlined below in section 16.5.

Assessment and reporting will be undertaken in line with the requirements of the Sponsor, Monash Health and the National Health Medical Research Council (NHMRC)⁵⁸. For this trial, it is a stipulation of Monash Health Human Research Ethics Committee (HREC) that if a participant experiences a serious adverse event that is related/possibly related/unknown if related to the study drug, a report will be provided to the HREC and a copy will also be forwarded to the Pharmacy.

All AE/SAE will be recorded from the time of signing the consent form, until the participant has completed all trial related follow-up procedures i.e. until all follow-up visits and assessments of the child at approximately 2 years corrected age have been completed.

All observed or volunteered AE/SAE regardless of causal relationship will be recorded and reported. These events may be declared by the participant or legal guardian and/or identified in response to an open-ended question from the researchers or revealed by observation, physical examination, or while undertaking other trial related procedures.

The researchers are not obligated to actively seek AE/SAE in former trial participants. However, if the lead PI learns of any SAE, including a death, at any time after a participant or their child has been discharged from the trial, and the lead PI considers the event reasonably related to the trial participation, the PI would promptly notify the sponsor, Monash University. For all adverse events as detailed below, a notification email must be sent to [contact], and enrolled patients will be alerted to this.

16.2 – Definitions

16.2.1 - Adverse Event (or Adverse Experience)

Any untoward medical occurrence in a participant or clinical investigation participant administered a pharmaceutical product and which does not necessarily have to have a causal relationship with this treatment.

An adverse event (AE) can therefore be any unfavourable and unintended sign (including an abnormal laboratory finding, for example), symptom, or disease temporally associated with the use of a pharmaceutical product, whether or not considered related to the pharmaceutical product.

16.2.2 - Adverse Drug Reaction (ADR)

For *marketed pharmaceutical products*, a definition of an adverse drug reaction in the post marketing setting is found in the Australian Code for the Responsible Conduct of Research 59:

“A response to a drug which is noxious and unintended and which occurs at doses normally used in man for prophylaxis, diagnosis, or therapy of disease or for modification of physiological function” p28.

The old term "side effect" has been used in various ways in the past, usually to describe negative (un-favourable) effects, but also positive (favourable) effects. It is recommended that this term no longer be used and particularly should not be regarded as synonymous with adverse event or adverse reaction.

16.2.3 - Serious Adverse Event (SAE) or Adverse Drug Reaction (ADR)

During the conduct of the trial, adverse events may occur which, if suspected to be related to the pharmaceutical product administered (adverse drug reactions), might be significant enough to lead to important changes in the way the pharmaceutical product is used (e.g. change in dose, population, monitoring required, consent forms). This is particularly true for reactions that, in their most severe forms, threaten life or function. Such reactions will be reported promptly to the sponsor, Monash Health and if necessary also the VMIA and TGA.

To ensure no confusion or misunderstanding of the difference between the terms "serious" and "severe," which are not synonymous, the following note of clarification is provided:

The term "severe" is often used to describe the intensity (severity) of a specific event (as in mild, moderate, or severe myocardial infarction); the event itself, however, may be of relatively minor medical significance (such as severe headache). This is not the same as

"serious," which is based on participant/event outcome or action criteria usually associated with events that pose a threat to a participant's life or functioning. Seriousness (not severity) serves as a guide for defining regulatory reporting obligations.

A serious adverse event (experience) or reaction is any untoward medical occurrence that at any dose:

- 1) Results in death
- 2) Is life-threatening
- 3) Requires hospitalisation or prolongation of hospitalisation
- 4) Results in persistent or significant disability/incapacity
- 5) Is a congenital anomaly/birth defect
- 6) Is an important medical event

The term "*life-threatening*" in the definition of "serious" refers to an event in which the participant was at risk of death at the time of the event; it does not refer to an event, which hypothetically might have caused death if it were more severe.

The term *disability* means a substantial disruption of a person's ability to conduct normal life functions. This definition is not intended to include experiences of relatively minor medical significance such as: uncomplicated headache, nausea, vomiting, diarrhoea, influenza, and accidental trauma (e.g. sprained ankle) which may interfere or prevent everyday life functions but do not constitute a substantial disruption.

Important Medical Event: Medical and scientific judgment should be exercised in deciding whether expedited reporting is appropriate in other situations, such as important medical events that may not be immediately life-threatening or result in death or hospitalisation but may jeopardize the participant or may require intervention to prevent one of the other outcomes listed in the definition above. These should also usually be considered serious. Examples of such events are intensive treatment in an emergency room or at home for allergic bronchospasm; blood dyscrasias or convulsions that do not result in hospitalisation; or development of drug dependency or drug abuse.

16.2.4 - Suspected Unexpected Serious Adverse Reactions (SUSAR)

Melatonin is a marketed medical product thus an unexpected drug reaction will be defined as a response that is noxious and unintended and which occurs at doses normally used for prophylaxis, diagnosis or therapy of diseases or for modification of physiological function. The reaction will be considered unexpected in nature if the nature or severity of which is not consistent with the applicable scientific information e.g. Product Information document or similar for this product.

The named Lead principal investigator with responsibility for trial related medical decisions will be responsible for determining whether an adverse drug reaction is expected or unexpected.

16.3 - Assessment of Severity/Intensity

Severity and seriousness must be differentiated. Severity describes the *intensity* of an AE, while the term *seriousness* refers to an AE that has met the criteria for an SAE as described above.

The investigator will make an assessment of *intensity* for each AE and SAE reported during the trial and will assign it to one of the following categories:

- *Mild*: an event that is easily tolerated, requires minimal or no treatment, causes minimal discomfort and does not interfere with the participant's daily activities.
- *Moderate*: events result in a low level of inconvenience or concerns with the pharmaceutical product, minimal, local, or non-invasive intervention indicated. Moderate events may cause some interference with normal everyday activities/functioning.
- *Severe*: events interrupt a participant's usual daily activity and may require the participant to seek and receive medical attention, systemic drug therapy or other treatment. Severe events are usually incapacitating.

Changes in the severity of an AE should be documented to allow an assessment of the duration of the event at each level of intensity to be performed. Adverse events characterized as intermittent require documentation of onset and duration of each episode if the severity of the intermittent event changes. An AE that is assessed as severe will not be confused with an SAE. *Severity* is a category utilized for rating the intensity of an event; and both AEs and SAEs can be assessed as severe. An event is defined as 'serious' when it meets at least one of the pre-defined outcomes as described in the definition of an SAE.

16.4 - Assessment of causality

All adverse events must have their relationship to trial intervention (melatonin) or trial participation assessed as either related or not related. Evaluation of relatedness must consider etiologies such as natural history of the underlying disease, concurrent illness, concomitant therapy, trial-related procedures, accidents, and other external factors.

To assess relationship of an event to the trial drug (melatonin), the following guidelines will be used:

- *Not related (unrelated)*: This relationship suggests that there is no association between the trial drug and the reported event.
- *Unlikely related*: This relationship suggests that the clinical picture is highly consistent with a cause other than the trial drug but attribution cannot be made with absolute

certainty and a relationship between the trial drug and AE cannot be excluded with complete confidence.

- *Possibly related:* This relationship suggests that treatment with the trial drug may have caused or contributed to the AE, i.e., the event follows a reasonable temporal sequence from the time of drug administration and/or follows a known response pattern to the trial drug, but could also have been produced by other factors.
- *Probably related:* This relationship suggests that a reasonable temporal sequence of the event with the trial drug administration exists and the likely association of the event with the trial drug. This will be based upon the known pharmacological action of the trial drug, known or previously reported adverse reactions to the trial drug or class of drugs, or judgment based on the Principal Investigator's clinical experience.
- *Definitely related:* Temporal relationship to the trial drug. Other conditions (concurrent illness, concurrent medication reaction, or progression/expression of disease state) do not appear to explain event, corresponds with the known pharmaceutical profile, improvement on discontinuation, re-appearance on re-challenge.

16.5 - Recording and reporting adverse events and reactions to the Sponsor

16.5.1 - Suspected Unexpected Serious Adverse Reactions (SUSAR)

SUSAR (Suspected Unexpected Serious Adverse Reaction) that occur with a Monash Health participant or with a participant from a site that Monash Health has provided HREC Review through multi-site trial approval are to be reported to Research Support Services within 24 hours.

These events are reported on the SUSAR/USADE site report available at: <http://www.health.vic.gov.au/clinicaltrials/application-instructions.htm>

All SUSAR that are reported to Research Support Services will require an action plan from the investigator, specifying what action is being undertaken and a follow up report within 30 days of reporting. If Investigators suspect an adverse event may be a SUSAR, they should report it immediately to the TGA.

For SUSAR, it is mandatory to include the UR number, date of birth and participants initials as the SUSAR report is forwarded to the VMIA.

16.5.2 - Serious Adverse Events (SAEs)

All SAE that occur with a Monash Health participant or with a participant from a site that Monash Health has provided HREC Review through multi-site trial approval, which are considered by the investigator as being definitely related, probably related, possibly related and unknown are to be reported within 72 hours to Research Support Services.

These reports for AE and SAE are available at:
<http://www.health.vic.gov.au/clinicaltrials/application-instructions.htm>

All SAE that are reported will require an action plan from the investigator, specifying what action is being undertaken and a follow up report is to be provided within 30 days of the initial report.

SAE should be reported immediately to the sponsor and the TGA, except for those SAE that the protocol identifies as not needing immediate reporting.

In the event of a death of a trial participant, sites should follow local site recommendations in addition to completing an SAE report. For example, for Monash Health participants, it is also mandatory for the death notification to be entered into the Riskman module.

16.5.3 - Adverse Events (AE)

The reporting of AE is at the discretion of the investigator based on whether the investigator is concerned that the adverse event poses a safety risk.

In addition, if the researchers or the sponsor is of the opinion that an adverse event, which is not graded 3 or above but poses a safety risk, should also be reported. Adverse events must be reported to the Research Support Services, Monash Health within 60 days of the date of the researcher learning of the event. These reports are available at:

<http://www.health.vic.gov.au/clinicaltrials/application-instructions.htm>

16.6 - Line Listings

 - Compromise of confidentiality of data, such as protocol violations, unblinding etc.
 - Scientific or therapeutic advances that may impact on participant safety or the ethics of the study

We would advise the DSMC to advocate complete cessation, or re-evaluation, of the trial conduct, if it is evident that either arm of the trial is associated with a statistically significant increase in or a 50% increased rate above the baseline ratio of any adverse events.

16.7.3 - Information presented to the DSMC

All data will be presented to the DSMC without any participant personal identifiers associated with it. The interim analysis results will not be available to anyone external to the DSMC unless the trial is required to cease prematurely.

16.7.4 - Frequency of DSMC reporting

We will provide information to the DSMB following the recruitment of 100 participants and again following recruitment of 200 participants. Information will be provided at other times if requested by the DSMC or the Sponsor, Monash Health Research Directorate and Human Research Ethics Committee. No interim statistical analyses of the primary or secondary outcomes are planned.

16.7.5 - Notification to the Monash Health Research Directorate and HREC of DSMC findings

The Lead PI will notify the sponsor, Monash Health Research Directorate and the Human Research Ethics Committee, of the DSMC's findings at each of the safety assessment time points.

The Lead PI will notify the DSMC of all SAE/AEs submitted to the sponsor, Monash Health.

16.8 - Reporting to Research Support Services

Forms will be emailed to Research Support Services at:
[contact]

AE correspondence will be included in the next HREC agenda. Within a week of the meeting, acknowledgement will be forwarded to the Lead Principal Investigator and Study Coordinator. In order to respond to researchers in a timely manner, the Research Support Services will not send a formal letter. Instead, the cover letter/report form submitted by the researcher will be signed and dated by the HREC Chair or designee. A copy of the stamped letter will be scanned to the Lead Principal Investigator and Study Coordinator as verification.

16.9 - Events that will not be reported

It may be the events may occur that are not related to the trial or therapeutic intervention. Such as, prolongation of hospitalisation for a reason that is not related to trial participation e.g. social reasons. The details surrounding these events will be assessed by the Lead Principal Investigator and if deemed not-related, they will not be reported. The details of these events will however be stored.

17. MONITORING OF TRIAL PROGRESS

Regular progress reports will be circulated to all local investigators on a bimonthly basis. Reports will include information such as number of participants recruited, number of participants completing the trial and any AE or SAE that have been assessed as being directly attributed to trial participation.

18. PROPOSED TIMELINE

August 2017 – August 2018

Protocol preparation, Monash Health ethics, recruitment of further centres both nationally and internationally

October 2017 – April 2018

Grant applications to major funding bodies, recruitment of trial co-ordinator and research midwife, purchase and packaging of trial intervention.

Submission to Monash Health HREC

Set-up of trial database and randomisation service.

May 2019

Commence recruitment

Ongoing data collection

December 2023

End recruitment

January – June 2024

Perform laboratory analysis to determine the impact of melatonin on oxidative stress within the mother, fetus and placenta.

Analyse data regarding the safety and tolerability in mother and fetus

December 2025

Complete 2-year follow-up neurodevelopmental assessments and data collection.

January – April 2026

Complete data analysis

Publication preparation

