6. TRIAL POPULATION

Pregnant women with a singleton pregnancy complicated by severe fetal growth restriction identified at 23+0 – 31+6 weeks' gestation will be approached for recruitment.

6.1 - Inclusion Criteria

1. Singleton Pregnancy
2. Severe fetal growth restriction, defined as:
 - Abdominal circumference \leq 3rd centile for gestational age according to charts supplied that have been adapted from Westerway et al ⁵²; or
 - Abdominal circumference $<$ 10th centile ⁵² in combination with at least one abnormal fetoplacental Doppler study, being:
 - Uterine artery (raised pulsatility index \geq 95th centile)⁵³
 - Umbilical artery (pulsatility index \geq 95th centile⁵⁴ or absent/reversed end-diastolic flow)
3. Confirmed 23+0 – 31+6 weeks' gestation
4. Age \geq 18 years
5. Understand English

6.2 - Exclusion Criteria

1. A fetus with a known chromosomal, major structural anomaly or non-placental cause of fetal growth restriction
2. Pregnancies requiring immediate delivery (e.g. absent A wave in ductus venosus, preterminal CTG or biophysical profile)
3. Co-recruitment in another clinical trial where a pharmaceutical product or nutritional supplement impacting on oxidative stress is the trial intervention.
4. Currently prescribed Fluvoxamine

6.3 - Withdrawal of Trial Participants

All participants are free to withdraw from the trial at any point if they wish. The study power calculation allows for a 5% drop-out rate. This drop-out rate is a conservative estimate of what has been observed in other clinical trials performed within our institution. Ongoing clinical care will continue as determined by the treating clinical team following best practice

guidelines. Data collected to the point of withdrawal will be retained unless the participant specifically advises against this.

Pregnancy, birth and postnatal outcome data will be collected from the participant's hard copy clinical notes, relevant Hospital databases and directly from the participant. Data related to the baby/child will similarly be collected from hard copy clinical notes and relevant Hospital databases. If the participant chooses to discontinue the trial intervention, participation in sample collection at birth and the neonatal outcome follow-up will still be offered.

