10. TRIAL STUDY GROUPS

10.1 – Trial Study Groups

Once informed, written consent has been obtained, participants will be stratified by gestational age. Hereafter, participants will subsequently be randomized into one of two groups to receive the trial intervention, either:

1. Melatonin
10mg melatonin tablets, administered three times a day (tds) (a total daily dose of 30mg per day) **or**
2. Placebo
Visually identical placebo tablets containing no active ingredient, administered three times a day (tds)

Participants, their healthcare providers and the research team will be blinded to the trial intervention the participant has received throughout the trial and during follow-up of the children until all participants have completed all the stages of the trial as per protocol.

10.2 – Drug Supply and Storage

Melatonin 10mg tablets with a Certificate of Analysis will be sourced by Akesa Pharma (Melbourne, Australia). A matched placebo will then be produced by the Pharmaceutical Packaging Professionals (Port Melbourne, Australia), who will repack all trial medication to maintain blinding and manage its storage and distribution. Trial medication will be supplied in bottles containing 42 tablets to cover trial medication for a 2-week period. Trial medication will then be dispensed to participating sites designated trial pharmacies for dispensing to the individual trial participants on a fortnightly basis.

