12.5 Neurodevelopmental Assessments

Neurodevelopmental assessments will be performed using a General Movement Assessment (GMA), magnetic resonance imaging (MRI), Bayley Scales of Infant and Toddler Development 4th edition (Bayley-4) and the Infant Toddler Social-Emotional Assessment (ITSEA). GMA and MRI will be performed at term corrected, GMA will be repeated a further two times at 3 months corrected age ± 2 weeks, while Bayley-4 and ITSEA will be performed at 24-36 months corrected age. If participants are enrolled in concurrent studies where the same assessments are involved, or if the clinical team has flagged for this assessment to be complete, patient data will be shared between research and/or clinical teams to minimise the inconvenience for the participants. The research team will seek formal consent for this data sharing arrangements from these participants.

12.5.1 - GMA

GMA is a non-invasive measure of spontaneous infant movement. Episodes of spontaneous movements are assessed via video recordings using established methodology⁵⁷, with movements classified as normal, abnormal, or absent depending on the gestational age of the

infant and number of weeks post birth. While a simple measure that is easily learned, it has been shown to be a clinically useful indicator of an individual's likelihood of developing cerebral palsy with high positive and negative predictive values. This assessment is not currently in routine clinical use across all health services. All GMA's will be collected using the Baby Moves App (Murdoch Children's Research Institute) and assessed by assessors blinded to treatment group. One GMA will be collected at term equivalent, then two separate video's collected at 3 months corrected age a couple of weeks apart to assist the GMA assessors in reliably determining a reduction or absence of fidgety movements. For sites where the GMA is part of routine care and with established clinical follow-up pathways in place, GMA results will be available to the treating team and additional interventional care offered if indicated, as is usual practice at Monash Health. The research team will not be involved in this care or the decisions regarding the need for interventional therapy. However, at sites where the GMA is not clinically used, results will not be disclosed.

12.5.2 – MRI

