The primary outcome is a clinically meaningful difference in cognitive development at 24-36 months corrected age identified by a change in the Bayley-4 Cognitive score of 5 points. We will administer the cognitive, language and motor domains of the Bayley-4. The Bayley-4 is a direct assessment of neurodevelopment and will be performed by an experienced paediatric developmental psychologist blinded to (i) treatment group and (ii) GMA scores. Any concerning results will be discussed with the family and when appropriate referral onto appropriate specialists/services made.

12.5.4 – ITSEA

The ITSEA assesses a wide array of social-emotional and behavioural problems and competencies. It is validated for use between 12-36 months of age and will be applied to our trial cohort at 24-36 months corrected age. It is a parent-reported assessment undertaken in the form of a questionnaire. Results will be analysed by an experienced paediatric developmental psychologist blinded to treatment group, GMA and Bayley-4 data.

Any concerning results will be discussed with the family and when appropriate referral onto appropriate specialists/services made.

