12.7 Outcome data collection

The researcher will collect relevant data regarding pregnancy outcomes from the maternal clinical record (hard copy and online hospital databases). Neonatal and child (up to 3 years) outcome data will be collected from the hospital records (hard copy and online hospital records) from the time of birth up to 3 years corrected age. Consent will also be sought to access longer term childhood outcome data, such as educational performance. If participants are enrolled in concurrent studies where the same assessments are involved, or if the clinical team has flagged for particular common assessments to be complete, patient data will be shared between research and/or clinical teams to minimise the inconvenience for the

participants. The research team will seek formal consent for this data sharing arrangements from these participants.

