14. OUTCOME MEASURES

14.1 - Primary Outcome

Improved neurodevelopmental performance at 2 years of life among survivors of early onset FGR.

The ability of melatonin to protect the fetal brain in the setting of severe early-onset fetal growth restriction will be assessed by multiple assessments across the first 2 years of life. The trial is powered to detect a difference in neurodevelopmental performance at 24-36 months corrected age on the Bayley-4. Other tools of assessing brain development and neurocognitive performance will also include GMA and MRI at term, GMA again at 3-months corrected age and ITSEA at 24-36 months corrected age. These assessments will also be stratified depending on the fetal gestation and fetal Dopplers at the time of FGR diagnosis, with outcomes for those <28 weeks and between 28-31+6 weeks compared as a sub-analysis. Total mortality will be compared between melatonin and placebo.

14.2 - Secondary Outcomes

- Assessment of drug safety and tolerability: Maternal side effect profiles experienced, such as symptoms of drowsiness, abdominal cramps, flushing, migraines, gastrointestinal disturbance. This information will be collected from the participant medication diary.
- Maternal end-organ performance monitored through haematological and biochemical tests
- Fetal effects through assessing ultrasound parameters of fetal biometry (HC, BPD, AC and FL) and wellbeing (AFI, Doppler indices).

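### Does the December 2025 date for completing follow-up cut off the last recruits' 24-month assessments, and does the 2024 safety analysis break the blind?

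*Protocol*

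**What the plan says.** Section 18 starts recruitment in May 2019 and ends it in December 2023. It gives January-June 2024 for laboratory work and for this item: "Analyse data regarding the safety and tolerability in mother and fetus". December 2025 is the date for "Complete 2-year follow-up neurodevelopmental assessments and data collection", and January-April 2026 is for the final data analysis.

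The rules that these dates must serve are elsewhere in the protocol:

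- **Entry (Section 6):** "Pregnant women with a singleton pregnancy complicated by severe fetal growth restriction identified at 23+0" up to 31+6 weeks.
- **Primary instrument (Section 12.5):** "while Bayley-4 and ITSEA will be performed at 24-36 months corrected age". Sections 12.5.3 and 14.1 give the same window.
- **Assessor (Section 12.5.3):** the Bayley-4 "will be performed by an experienced paediatric developmental psychologist blinded to (i) treatment group and (ii) GMA scores".
- **Records (Section 12.7):** child outcome data are taken from hospital records "from the time of birth up to 3 years corrected age".
- **Blind (Section 10.1):** participants, their carers and the research team stay blinded throughout the trial and "during follow-up of the children until all participants have completed all the stages of the trial as per protocol".
- **Safety outcome (Section 14.2):** the first secondary outcome is "Assessment of drug safety and tolerability: Maternal side effect profiles experienced".
- **Interim analysis (Section 16.7.4):** none is planned for the primary or secondary outcomes.

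**The concern.** Two things look wrong.

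First, December 2025 is exactly 24 months after December 2023, but the assessment is timed by corrected age. A woman recruited in December 2023 is still 57 to 119 days short of 40+0, so her child's 24-month point falls in 2026. If a site treated December 2025 as a deadline, the last children would either be tested before the window opens or be missing from an analysis that starts in January 2026. That would affect the primary outcome.

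Second, an analysis of safety and tolerability in the first half of 2024 comes about 18 to 24 months before the stated end of follow-up. If it were done by arm within the trial team, the team would see comparative results on a secondary outcome while children were still being assessed.

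**Working it through.** **1. Where December 2025 comes from.** End of recruitment, December 2023, plus 24 months gives December 2025. The date therefore counts from recruitment and not from the due date.

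**2. The date under the corrected-age rule.** The protocol does not define the reference for corrected age, so 40+0 (280 days) is assumed. Due date = recruitment date + (280 - gestation in days).

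| Recruited | Gestation | Days to 40+0 | Due date | 24 months corrected |
|---|---|---|---|---|
| 1 Dec 2023 | 31+6 (223 days) | 57 | 27 Jan 2024 | 27 Jan 2026 |
| 31 Dec 2023 | 23+0 (161 days) | 119 | 28 Apr 2024 | 28 Apr 2026 |

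Early delivery does not help, because corrected age runs from the due date. A lenient reference of 37+0 still gives 6 January 2026 at the earliest. The target is therefore about one to four months early for these children: 27 to 118 days after 31 December 2025.

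**3. How many women.** To reach 24 months corrected by 31 December 2025, recruitment had to occur by 4 November 2023 (at 31+6) or 3 September 2023 (at 23+0). That leaves the last 57 or 119 of the 1,706 days from 1 May 2019 to 31 December 2023. With even accrual:

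- 332 × 57/1706 = 11.1 women (3.3%)
- 332 × 119/1706 = 23.2 women (7.0%)

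With 166 women in each gestational stratum the range narrows:

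- below 28 weeks: 166 × (85 to 119)/1706 = 8.3 to 11.6
- 28 to 31+6 weeks: 166 × (57 to 84)/1706 = 5.5 to 8.2
- together: 13.8 to 19.8 women

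If accrual in those last days ran at half or double the earlier rate, the 11 to 23 becomes 6 to 12 or 21 to 43.

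**4. Worst case for power.** Section 7 plans 69 assessable children per arm in each stratum. A two-sided t test with difference 5, SD 9 and alpha 0.05 then has 90.0% power, which matches the protocol. Assessable children number 332 - 42 - 14 = 276, or 138 per stratum. Suppose every late child's outcome were missing:

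| Stratum | Children lost | Left per arm | Power |
|---|---|---|---|
| <28 weeks | 138 × (85 to 119)/1706 = 6.9 to 9.6 | 65.6 to 64.2 | 88.4% to 87.8% |
| 28 to 31+6 weeks | 138 × (57 to 84)/1706 = 4.6 to 6.8 | 66.7 to 65.6 | 89.0% to 88.5% |

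The whole-trial comparison starts at 138 per arm (99.6%). Losing 11.5 to 16.4 children leaves about 130 to 132 per arm, and power stays at 99.4%.

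**5. The 36-month limit.** The window is 24 to 36 months and one assessment inside it is enough, so children still under 36 months at the end of 2025 are not a shortfall. The 3 years in Section 12.7 is an outer limit for record collection, and the Section 18 entry is naturally read as referring to the 2-year data.

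**6. The 2024 safety analysis.** Section 18 does not say whether it is pooled or by arm. The outcomes in Section 14.2 are maternal side effects, maternal blood tests and fetal ultrasound, which are essentially complete at delivery. The last due date is 28 April 2024, so January-June 2024 is when those data become complete. Sections 10.1 and 16.7.4 already keep by-arm results from the team at that stage. A pooled summary, or an analysis held outside the team, satisfies all three sections. The laboratory work raises no conflict: under Section 24.2.2 samples are processed blind and linked to allocation only at data analysis.

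**The case for a change.** The best case for a change is that Section 18 is current text and the only place that dates the end of follow-up and the final analysis. Its dates cannot be met under the protocol's own assessment rule for any December 2023 recruit at any eligible gestation. The correction would be a line of wording, and it would guard the completeness of the primary outcome. On safety, no section says who performs the 2024 analysis or whether it is pooled, and the committee reviews at 100 and 200 recruits do not account for it.

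The date mismatch stands. The harm does not follow from it. For a child to be tested early or left out, staff would have to override a window repeated in several sections in favour of a calendar headed as proposed. The version history last records a timeline update in August 2022, while the current version is from July 2024, so this looks like a forecast that was not refreshed.

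On safety, what remains is silence about who analyses and how. That is ordinarily left to the statistical analysis plan, which is not shown here. Stating that the summaries are pooled would only repeat what Sections 10.1 and 16.7.4 require. The blinded Bayley-4 assessor gives the primary outcome further protection.

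**Conclusion.** No change to the plan follows. December 2025 is a scheduling slip: about one to four months too early for the children of the last recruits, affecting roughly 11 to 23 of 332 women if accrual was even and corrected age runs from 40+0. The assessment window governs, and it is stated consistently. Analysts following it would wait for the last children and let the final analysis run later, which costs calendar time and changes no estimate. Even the unlikely worst case, with every late outcome lost, costs about one to two points of power within a stratum and almost nothing overall. Updating the calendar is administrative housekeeping. The 2024 safety analysis is compatible with the blind as the rules already stand, and no by-arm analysis is stated, so it has no effect that can be sized.
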